8.3. Clinical Laboratory Analyses

Laboratory evaluations including the analyses of Chemistry/ Hematology/Other Laboratory tests, and liver function tests will be based on GSK Core Data Standards. The details of the planned displays are in [Appendix 10: List of Data Displays](#).

Endpoint / Parameter/ Display Type	Absolute			Change from BL		
	Summary		Individual	Summary		Individual
	T	F	L	T	F	L
Chemistry						
Chemistry Values by Visit	Y		Y	Y		
Percent change from baseline in Lipid Parameters ^[1] (total cholesterol, LDL cholesterol, HDL cholesterol, LDL/HDL cholesterol ratio) by Visit			Y	Y	Y	
Worst Case Chemistry Results Relative to Normal Range Post-Baseline Relative to Baseline	Y					
Worst Case Chemistry Results Relative to PCI Criteria	Y					

Endpoint / Parameter/ Display Type	Absolute			Change from BL		
	Summary		Individual	Summary		Individual
	T	F	L	T	F	L
Post-Baseline Relative to Baseline						
Hematology						
Hematology Values by Visit	Y		Y	Y		
Worst Case Hematology Results Relative to Normal Range Post-Baseline Relative to Baseline	Y					
Worst Case Hematology Results Relative to PCI Criteria Post-Baseline Relative to Baseline	Y					
Urinalysis^[3] (ND subjects only)						
Urinalysis Values by Visit	Y		Y	Y		
Worst Case Urinalysis Results Relative to Normal Range Post-Baseline Relative to Baseline	Y					
Iron Parameters						
Iron Values by Visit ^[4]	Y		Y	Y		
Worst Case Iron Results Relative to Normal Range Post-Baseline Relative to Baseline	Y					
Worst Case Iron Results Relative to PCI Criteria Post-Baseline Relative to Baseline	Y					
Other Laboratory Tests ^[2]						
Other Laboratory Values by Visit	Y		Y	Y		
Worst Case Other Laboratory Results Relative to Normal Range Post-Baseline Relative to Baseline	Y					
Worst Case Other Laboratory Results Relative to PCI Criteria Post-Baseline Relative to Baseline	Y					
Hepatobiliary (Liver)						
Liver Monitoring/Stopping Event Reporting	Y					
Hepatobiliary Laboratory Abnormalities	Y					
Medical Conditions for Subjects with Liver Stopping Events			Y			
Substance Use for Subjects with Liver Stopping Events			Y			
Scatter Plot of Maximum vs. Baseline for ALT		Y				
Scatter Plot of Maximum ALT vs Maximum Total Bilirubin		Y				
All Laboratory						
All Laboratory Data for Subjects with any Value of Potential Clinical Concern/PCI			Y			
Laboratory Values of PCI			Y			

NOTES:

- T = Table, F = Figures, L = Listings, Y = Yes display generated, PCI = Potential Clinical Importance
- Summary = Represents TFL related to any summaries (i.e. descriptive statistics) of the observed raw data.
- Individual = Represents FL related to any displays of individual subject observed raw data.

[1] Lipid parameters will be log-transformed and the percent change from baseline will be reported.

[2] iPTH and eGFR will be collected as other laboratory tests

[3] Urine creatinine, urine albumin, urine albumin/creatinine ratio

[4] Transferrin and UIBC will be included for this summary and other iron parameters will be provided as efficacy endpoints.

8.3.1. Planned Clinical Laboratory Analyses Displays

LDL/HDL cholesterol ratio will be derived from LDL and HDL cholesterol (see Section 15.6.4), and handled as one of chemistry laboratory tests and lipid parameters.

- ***Chemistry/Hematology/Urinalysis/Iron Parameter/Other Laboratory Tests***

Clinical Laboratory Values by Visit

The values will be summarized using mean, standard deviation, median, minimum, and maximum at each assessment visit and baseline by treatment group. Chemistry values, hematology values, iron parameters, urinalysis values, and other laboratory values will be summarized separately.

Percent change in Lipid Parameters

Lipid parameters will be log-transformed and the percent change from baseline will be reported. The percent change from baseline in each lipid parameter, including baseline values, will be summarized using geometric mean, 95% CI, minimum, median, and maximum at each assessment visit by treatment group. In baseline values, the coefficient of variation will also be provided.

Clinical Laboratory Changes from Baseline by Visit

The values will be summarized using mean, standard deviation, median, minimum, and maximum at each assessment visit. Change from baseline in chemistry, hematology, urinalysis, iron parameter, and other laboratory will be summarized separately.

Worst Case Laboratory Results Relative to Normal Range/PCI Criteria Post-Baseline Relative to Baseline

The number and percentage of subjects with worst case laboratory results relative to normal range/potential clinical importance (PCI) criteria which are post-baseline relative to baseline, including unscheduled assessments, will be summarized by test and category by treatment group. Summaries for normal range and PCI will be provided separately. The categories for normal range are: To Low, To Normal or No Change, To High; the categories for PCI criteria are: To Low, To w/in Range or No Change, To High. The categorization is determined by comparing the baseline category to the worst case post-baseline category. PCI Criteria is described in [Appendix 8](#).

- ***Hepatobiliary (Liver)***

Details of liver chemistry stopping criteria are described in the protocol.

Liver monitoring/stopping events will be summarized by treatment group.

Hepatobiliary laboratory abnormalities will be summarized by treatment group.

A scatter plot of maximum on-therapy ALT values versus baseline ALT values will be produced if larger data permit.

A scatter plot of maximum total bilirubin (xULN) versus maximum ALT (xULN) values on-therapy will be produced if larger data permit.

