15.6. Appendix 6: Derived and Transformed Data

15.6.1. General

Multiple Measurements at One Analysis Time Point

 Subjects having both High and Low values for Normal Ranges at any post-baseline visit for safety parameters will be counted in both the High and Low categories of “Any visit post-baseline” row of related summary tables. This will also be applicable to relevant PCI summary tables. For multiple measurements at Screening and/or Day 1 visit, the screening pass visit record will be used for analysis (See Appendix 3: Assessment Windows)
Study Day

 Calculated as the number of days from Randomization Date: 
 Ref Date = Missing → Study Day = Missing Ref Date < Randomization Date → Study Day = Ref Date - Randomization Date Ref Date ≥ Randomization Date → Study Day = Ref Date - (Randomization Date) + 1
Unique Subject ID

 All subjects have unique subject ID for analyses even if a subject was enrolled after rescreened. Tables/figures/listings will be produced based on unique subject ID. For a rescreened subject, the unique subject ID will be derived from the first-assigned subject number though he or she seems to have different subject numbers in eCRF by screening assessments.
Rescreening Subjects

 For rescreened subjects, data collected in screening-pass visit will be used for analysis. They may have multiple records at Screening and/or Day 1 visit, which associates with a screening-pass visit and screening failure visit(s) Regarding a listing of SAEs in screening period, all pre-therapy SAEs captured in eCRF will be provided including screen failure records of rescreened subjects.
Treatment Start Date

 First randomized treatment start date
Treatment Stop Date - Daprodustat

 Calculated as the latest treatment stop date.
Treatment Stop Date – Epoetin Beta Pegol

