15.8. Appendix 8: Values of Potential Clinical Importance

15.8.1. Laboratory Values

Chemistry			
Laboratory Parameter	Units	Clinical Concern Range	
		Low Flag	High Flag
Albumin (serum)	g/L	< 30 g/L	>55 g/L
Aspartate Aminotransferase	IU/L	N/A	≥ 3x ULRR
Alanine Aminotransferase	IU/L	N/A	≥ 3x ULRR
Bilirubin (total)	μmol/L	N/A	≥ 2x ULRR
Calcium (albumin-adjusted)	mmol/L	< 1.87 mmol/L	> 2.56 mmol/L
Bicarbonate (total)	mmol/L	< 20 mmol/L	> 32 mmol/L
Inorganic phosphate	mmol/L	< 0.81 mmol/L	> 1.77 mmol/L
Potassium (serum)	mmol/L	> 0.5 mmol/L below LLRR	> 1.0 mmol/L above ULRR
Sodium (serum)	mmol/L	< 130 mmol/L	> 150 mmol/L

Hematology			
Laboratory Parameter	Units	Clinical Concern Range	
		Low Flag	High Flag
Platelet Count	GI/L	< 80 GI/L	> 500 GI/L
WBC Count	GI/L	> 1x LLRR	>5x ULRR
Neutrophils	GI/L	< 1.0 GI/L	N/A
Lymphocytes	GI/L	< 0.5 GI/L	N/A

Iron Parameters			
Laboratory Parameter	Units	Clinical Concern Range	
		Low Flag	High Flag
Ferritin	μg/L	< 100 μg/L	> 1200 μg/L
TSAT	%	<15 %	>40 %

Urinalysis Parameters			
Laboratory Parameter	Units	Clinical Concern Range	
		Low Flag	High Flag
Urine albumin/creatinine ratio	g/mol		> 3.4 g/mol

Other Parameters			
Laboratory Parameter	Units	Clinical Concern Range	
		Low Flag	High Flag
iPTH	ng/L	N/A	> 9x ULRR
eGFR	mL/min/1.73m ²	≥ 40% decrease from baseline	

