3.81.	Safety	LB1	Summary of Hematology Changes from Baseline by Visit – ND Subjects	ICH E3	Y
3.82.	Safety	LB1	Summary of Hematology Changes from Baseline by Visit – PD Subjects	ICH E3	Y
3.83.	Safety	LB15	Summary of Worst Case Hematology Results Relative to Normal Range Post-Baseline Relative to Baseline – ND Subjects	ICH E3	Y
3.84.	Safety	LB15	Summary of Worst Case Hematology Results Relative to Normal Range Post-Baseline Relative to Baseline – PD Subjects	ICH E3	Y

CONFIDENTIAL

201753

Safety Tables					
No.	Population	IDSL / TST ID / Example Shell	Title	Programming Notes	SAC
3.85.	Safety	LB17	Summary of Worst Case Hematology Results Relative to PCI Criteria Post-Baseline Relative to Baseline – ND Subjects	ICH E3	Y
3.86.	Safety	LB17	Summary of Worst Case Hematology Results Relative to PCI Criteria Post-Baseline Relative to Baseline – PD Subjects	ICH E3	Y
Urinalysis					
3.87.	Safety	LB1	Summary of Urinalysis Values by Visit – ND Subjects	ICH E3 Includes Baseline values	Y
3.88.	Safety	LB1	Summary of Urinalysis Changes from Baseline by Visit – ND Subjects	ICH E3	Y
3.89.	Safety	LB15	Summary of Worst Case Urinalysis Results Relative to Normal Range Post-Baseline Relative to Baseline – ND Subjects	ICH E3	Y
3.90.	Safety	LB17	Summary of Worst Case Urinalysis Results Relative to PCI Criteria Post-Baseline Relative to Baseline – ND Subjects	ICH E3	Y
Iron Parameters					
3.91.	Safety	LB1	Summary of Iron Values by Visit – ND Subjects	ICH E3 Includes Baseline values	Y
3.92.	Safety	LB1	Summary of Iron Values by Visit – PD Subjects	ICH E3 Includes Baseline values	Y
3.93.	Safety	LB1	Summary of Iron Changes from Baseline by Visit – ND Subjects	ICH E3	Y
3.94.	Safety	LB1	Summary of Iron Changes from Baseline by Visit – PD Subjects	ICH E3	Y
3.95.	Safety	LB15	Summary of Worst Case Iron Results Relative to Normal Range Post-Baseline Relative to Baseline – ND Subjects	ICH E3	Y
3.96.	Safety	LB15	Summary of Worst Case Iron Results Relative to Normal Range Post-Baseline Relative to Baseline – PD Subjects	ICH E3	Y

CONFIDENTIAL

201753

Safety Tables					
No.	Population	IDSL / TST ID / Example Shell	Title	Programming Notes	SAC
3.97.	Safety	LB17	Summary of Worst Case Iron Results Relative to PCI Criteria Post-Baseline Relative to Baseline – ND Subjects	ICH E3	Y
3.98.	Safety	LB17	Summary of Worst Case Iron Results Relative to PCI Criteria Post-Baseline Relative to Baseline – PD Subjects	ICH E3	Y
Other Laboratory Tests					

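### The white-cell PCI Low flag in Appendix 8 points the wrong way, so the WBC row of Tables 3.85 and 3.86 cannot show a fall below the lower limit and reports a recovery as To Low

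*SAP*

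**What the plan says.** SAP Section 8.3.1 defines the worst-case laboratory displays. For the PCI version, "the categories for PCI criteria are: To Low, To w/in Range or No Change, To High", and the rule for placing a subject is "The categorization is determined by comparing the baseline category to the worst case post-baseline category". The limits are not in that section: "PCI Criteria is described in" Appendix 8. The same section adds that "Summaries for normal range and PCI will be provided separately".

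Appendix 8 (Section 15.8.1, Hematology) gives WBC a Low flag of greater than 1x LLRR and a High flag of greater than 5x ULRR. The other three Low flags in that block use a less-than sign: platelets below 80, neutrophils below 1.0 and lymphocytes below 0.5 GI/L. In the chemistry block, potassium has the only other Low flag that sets a greater-than sign against LLRR, and it carries the word that makes it work: "> 0.5 mmol/L below LLRR".

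The limits feed Tables 3.85 and 3.86 in Section 15.10.4.4, titled "Summary of Worst Case Hematology Results Relative to PCI Criteria Post-Baseline Relative to Baseline" for ND and PD subjects respectively. Section 15.6.1 has subjects with both High and Low normal-range values counted in both categories, and says of this: "This will also be applicable to relevant PCI summary tables".

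**The concern.** A Low flag should pick out values that are too low. This one picks out everything above the lower reference limit, which includes the normal range above that limit. The shift rule in Section 8.3.1 is sound, but it takes its categories from Appendix 8 and carries the inverted flag into the tables. Nothing else in the SAP corrects it. Amendment 1 revised Appendix 8 to add an eGFR value, and the current text still has the WBC entry.

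At stake is one parameter in one pair of planned safety tables. In that row a recovery would be counted as a deterioration, and a new fall below LLRR would be counted with the unchanged subjects.

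**Working it through.** **Inputs.** From Appendix 8: WBC Low if the value exceeds 1x LLRR; High if it exceeds 5x ULRR. From Section 8.3.1: compare the baseline category with the worst post-baseline category. From Section 15.6.1: a subject meeting both flags is counted in both. The SAP gives no LLRR or ULRR for WBC, so values are in multiples of LLRR, and the ratio ULRR/LLRR is assumed to be 2, 2.5, 3 or 4.

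**Step 1, the logic.** Write L for LLRR, b for the baseline value and p for the post-baseline value. As printed, a subject is To Low when the baseline is not Low (b ≤ L) and the post-baseline value is Low (p > L). Together these give p > b. Every To Low is therefore a rise, whatever L is, and no fall can qualify.

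**Step 2, typical courses.** The results are the same at all four assumed ratios.

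| Course (multiples of LLRR) | Baseline category as printed | Shift as printed | Shift if Low means below LLRR |
|---|---|---|---|
| 1.5, then 1.4 and 1.6 | Low | w/in Range or No Change | w/in Range or No Change |
| 1.5, then 0.6 | Low | w/in Range or No Change | To Low |
| 1.5, then 1.4 and 0.6 | Low | w/in Range or No Change | To Low |
| 0.6, then 1.5 | Within | To Low | w/in Range or No Change |
| 0.8, then 0.4 | Within | w/in Range or No Change | w/in Range or No Change |

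The last column shows direction only. It is not a proposed cut-off.

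**Step 3, a grid.** Take baseline and post-baseline values from 0.10 to 3.00 x LLRR in steps of 0.05, which is 59 values, with ratios 2, 3 and 4. Of these, 40 lie above 1 and 18 below, so each direction of crossing has 40 × 18 = 720 pairs, and 720 × 3 = 2160 over the three ratios.

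- Above LLRR to below LLRR: To Low in 0 of 2160.
- Below LLRR to above LLRR: To Low in 2160 of 2160.
- Falls of any size on the grid labelled To Low: 0.

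The High flag is never reached on this grid. Even at ratio 2 it starts at 5 × 2 = 10 x LLRR, so the assumed ratio cannot affect these counts.

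**Step 4, the top end.** A count above 5x ULRR is also above LLRR, so as printed it is both High and Low. If such a baseline were classed as High only, against the Section 15.6.1 convention, a drop from there to normal could read To Low. That rare case does not rescue the flag.

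**The case against.** The strongest reply is that this is a self-evident slip in one cell with little consequence. Much of that stands.

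- **A reader might infer that new leukopenia would be hidden.** The SAP does not support that beyond the WBC row of Tables 3.85 and 3.86. Tables 3.83 and 3.84 classify worst-case hematology against the normal range without using the PCI flag. By-visit values and changes (Tables 3.79 to 3.82) and the full hematology listing (Listing 69) are also planned, and the neutrophil and lymphocyte flags have the right sign. If the direction were corrected and the multiple of 1 kept, the PCI Low limit would be the lower reference limit itself, so the To Low row would largely repeat Tables 3.83 and 3.84.
- **A reader might infer that the comparison between arms is corrupted.** Table 3.86 covers a single-arm cohort and contains no such comparison. Table 3.85 is a descriptive count by arm, and only its WBC row is affected.
- **A reader might infer that Listing 46 would swell to nearly everyone because of this flag.** That cannot be attributed to the flag. The listing already takes any hematology value outside the normal range, and the trial enrols anemic subjects. Cohort 3 ESA non-users, for example, enter with Hgb from 8.0 to below 11.0 g/dL. The SAP gives no Hgb reference range, but any lower limit at or above 11.0 g/dL would select those subjects regardless of WBC.
- **The sign may not be what went wrong.** The potassium entry shows that a greater-than sign is legitimate when followed by the word below, so a dropped word is as possible as a reversed sign.

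A programmer might well notice that normal counts come out as Low. But the correction is not unique, and the SAP should not leave a safety threshold to a silent repair.

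**Conclusion.** The point holds in limited form. The WBC Low flag in Appendix 8 is wrong as written. Through the Section 8.3.1 rule, it makes the WBC row of Tables 3.85 and 3.86 blind to falls below LLRR and makes it report recoveries as To Low. The inversion follows from the printed inequality and does not depend on the unstated reference limits or on the assumed ULRR/LLRR ratio. It rests only on the flag being programmed literally, with subjects who meet both flags counted in both.

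The consequence is small: one row in two descriptive safety tables, plus the PCI-based part of the selection for Listing 46. No endpoint, test or category of adverse events of special interest depends on it. It is still worth correcting, because the threshold is operative and the correction costs almost nothing.

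**What to change.** In Appendix 8, restate the WBC Low flag so that it identifies values below the lower limit. The sponsor should establish whether the sign was reversed or the word below was lost, and reconcile the exact form and multiple of LLRR with its PCI standard and with the other hematology Low flags. No cut-off is proposed here. Section 8.3.1 needs no change.

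This should be done before Tables 3.85 and 3.86 and the PCI-based part of Listing 46 are programmed. If programs already exist, check the WBC line against the corrected entry. The cost is one table cell and the matching program line, with no effect on design, data collection or the efficacy analyses.

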8.4. Other Safety Analyses

The analyses of non-laboratory safety test results including ECGs and vital signs will be based on GSK Core Data Standards, unless otherwise specified. The details of the planned displays are presented in [Appendix 10: List of Data Displays](#).

Endpoint / Parameter/ Display Type	Absolute			Change from BL		
	Summary		Individual	Summary		Individual
	T	F	L	T	F	L
ECG						
ECG Findings	Y		Y			
ECG Values by Visit			Y	Y		
Abnormal ECG Findings			Y			
Vital Signs						
Vital Signs by Visit	Y		Y	Y		
Worst Case Vital Sign Results Relative to PCI Criteria Post-Baseline Relative to Baseline	Y					
All Vital Signs for Subjects with any Values of PCI			Y			
Ophthalmology						
Prior-Therapy Ophthalmologic Exams	Y		Y			
On-Therapy Ophthalmologic Exams	Y		Y			
Change in Anti-Hypertensive Medications						
Number (%) of Subjects who have any change in anti-hypertensive medications during treatment period	Y		Y			
Other						
Subjects who became pregnant during the study			Y			

NOTES:

- T = Table, F = Figures, L = Listings, Y = Yes display generated, PCI = Potential Clinical Importance
- Summary = Represents TFL related to any summaries (i.e. descriptive statistics) of the observed raw data.
- Individual = Represents FL related to any displays of individual subject observed raw data.

8.4.1. Planned Other Safety Analyses Displays

- *ECG*

ECG findings ('normal', 'abnormal, not clinically significant', 'abnormal, clinically significant') will be summarized by assessment visit for each treatment group. Change from baseline in ECG values will be summarized using mean, standard deviation, minimum, median, and maximum by assessment visit for each treatment group. Findings without regard to visits (labelled "Worst Case Post-Baseline", only the worst case finding for each subject) will also be provided. All ECG measures (heart rate, PR interval, QRS duration, QT [uncorrected] interval and QTcB [calculated], result of ECG) will be included in listings.

- ***Vital Signs***

Vital sign values will be summarized using mean, standard deviation, minimum, median, and maximum by assessment visit for each treatment group. Separate summary statistics of vital signs will be provided for raw values and change from baseline. In a summary of change from baseline, each baseline value will be used for calculation (Section 5.2).

The number of subjects with worst case vital sign results relative to PCI criteria which are post-baseline relative to baseline, including unscheduled assessments, will also be summarized by test and category by treatment group. The categories for PCI criteria are: To Low, To w/in Range or No Change, To High. The categorization is determined by comparing the baseline category to the worst case post-baseline category.

- ***Ophthalmology Exams***

The responses to each question and any questions will be summarized using number and percentage at each assessment visit by treatment group. The response will be classified into 'Yes' and 'No'. A summary of ophthalmology exams at screening and at on-therapy will be produced separately. The number and percentage of subjects with worst case after-screening ophthalmology exams (i.e., the response is 'Yes' at least once during whole treatment period, including unscheduled visits) will also be summarized by each question by treatment group.

- ***Change in Anti-Hypertensive Medications***

The number and percentage of subjects who have any change at least once in anti-hypertensive medications (type and/or dose) due to increased blood pressure during whole treatment period will be summarized by treatment group.

9. PATIENT REPORTED OUTCOME ANALYSES

9.1. Endpoint / Variables

Endpoint / Parameter/ Display Type	Absolute					
	Stats Analysis		Summary		Individual	
	T	F	T	F	F	L
Patient Reported Outcome						
SF-36 HR-QoL Scores (PCS, MCS, 8 subscales)			Y			Y
SF-36 HR-QoL Scores (PCS, MCS, 8 subscales) by Prior ESA Use			Y			
Changes from Baseline in SF-36 HR-QoL Scores (PCS, MCS, 8 subscales)	Y		Y			
Changes from Baseline in SF-36 HR-QoL Scores (PCS, MCS, 8 subscales) by Prior ESA Use	Y		Y			
EQ-5D-5L Scores			Y			Y
EQ-5D-5L Scores by Prior ESA Use			Y			
EQ-5D-5L Index Values			Y			Y
EQ-5D-5L Index Values by Prior ESA Use			Y			
Changes from Baseline in EQ-5D-5L Index Values	Y		Y			
Changes from Baseline in EQ-5D-5L Index Values by Prior ESA Use	Y		Y			
EQ VAS			Y			Y
EQ VAS by Prior ESA Use			Y			
Changes from Baseline in EQ VAS	Y		Y			
Changes from Baseline in EQ VAS by Prior ESA Use	Y		Y			

NOTES :

- T = Table, F = Figure, L = Listing, Y = Yes display generated.
- Stats Analysis = Represents TFL related to any formal statistical analyses (i.e. modelling) conducted.
- Summary = Represents TFL related to any summaries (i.e. descriptive statistics) of the observed raw data.
- Individual = Represents FL related to any displays of individual subject observed raw data.

9.2. Summary Measure

Scoring derivations are described in Section 15.6.7.

SF36 HR-QoL Scores and Changes from Baseline (PCS, MCS, 8 subscales)

The summary scores (PCS and MCS) and the domain scores (Physical Functioning [PF], Role-Physical [RP], Bodily Pain [BP], General Health [GH], Vitality [VT], Social Functioning [SF], Role-Emotional [RE], and Mental Health [MH]), and their changes from baseline will be summarized using mean, standard deviation, median, minimum, and maximum at each assessment visit by treatment group. For changes from baseline, the adjusted treatment difference and the 95% CIs will also be provided. The summary will also be provided by prior ESA use.

EQ-5D-5L / EQ VAS Scores and Changes from Baseline in EQ-5D-5L Index Value / EQ VAS

The number and percentage of subjects with each EQ-5D-5L score within each category will be displayed at each assessment visit by treatment group. EQ-5D-5L index values, EQ VAS scores, and their changes from baseline will be provided using mean, standard deviation, median, minimum, and maximum at each assessment visit by treatment group. The summary will also be provided by prior ESA use. For changes from baseline, the adjusted treatment difference and the 95% CIs will also be provided.

